7.4 Patients compliance and exit

To improve patient compliance, before randomization, physicians will communicate with patients in detail about surgical procedures, possible random groupings, relevant and evolving treatment, and patient safety and security conditions. They will obtain informed consent to ensure patients clearly understand the treatment and research procedures. The randomization time should be as close as possible to the time before surgery (the day before surgery) to prevent accidental exclusion of patients after randomization. After randomization, patients can withdraw from the trial at any time. If a patient requests withdrawal from the study, the main researcher at their research center will communicate with them to avoid disrupting the balance of random groups due to exclusion. If the patient still insists on withdrawing, they will be removed from the trial. Clinical information relating to this patient will not be included in any data analysis related to this trial.

7.5 Deviation from the plan

Researchers involved in the trial will conduct corresponding surgical operations and data recording in line with the experimental requirements. Any event that strays from the original test plan must record the time and specific reason for occurrence to explain the deviation from the test plan.

8 Evaluation

8.1 Efficacy Evaluation

The methodologies for evaluating the efficacy of diverse anastomosis techniques encompass, but are not restricted to: intraoperative assessment and meticulous records of postoperative examinations, evaluation of postoperative symptoms and signs, and postoperative abdominal CT evaluation.

8.2 Safety Assessment

8.2.1 Baseline Signs and Symptoms

The baseline signs and symptoms include temperature, pulse, respiratory rate, and blood pressure. Surgeons also need to pay attention to specific symptoms such as dizziness, nausea,

and vomiting. Additionally, hematological tests and imaging tests before surgery will be performed to ensure the patient group has no surgical contraindications and fully meets the inclusion criteria. These baseline data will serve as reference indicators for the evaluation.

8.2.2 Laboratory Safety Assessment

Continuous indicators show the postoperative measurements of each study subject and the changes in values compared to the preoperative baseline. Laboratory indicators are classified as low, normal, and high based on the normal value range. They describe transitions from a normal or high baseline to a low value after the baseline, and from a normal or low baseline to a high value after the baseline. The lower or higher value after the baseline is calculated using the minimum or maximum observed value. The physician evaluates these abnormal indicators to determine their clinical significance. The proportion of subjects with “abnormal and clinically significant” changes is described.

8.2.3 Physical Examination and Vital Signs

Physical examination includes general examination, head examination, neck examination, chest and lung examination, heart and blood vessels examination, abdominal examination, spine and limbs examination, and nervous system examination. Vital signs consist of blood pressure, heart rate, and body temperature. Situations where vital signs deviate from the normal range or are abnormal are described and recorded.

9. Adverse event report

9.1 Definition of adverse events

Adverse events studied include intraoperative secondary injuries in patients and serious complications and deaths within 30 days after surgery. All adverse events reported spontaneously by test subjects or observed by staff will be recorded in a database and promptly reported to the test steering committee.

An adverse event is defined as any adverse experience that occurs in the subject during the study, regardless of whether it's considered associated with total laparoscopic anastomosis. All adverse events reported spontaneously by test subjects or observed by investigators are

recorded. These include: 1) Accidental secondary damage during surgery. 2) Serious complications after surgery (grade III and above).

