5.3 Exit criteria

- (1) Patients with other non-tumor diseases that prevent them from continuing to receive this treatment regimen.
- (2) Patients who need emergency surgical resection due to intestinal obstruction, intestinal perforation, intestinal bleeding, etc. after being enrolled in the study.
- (3) Patients with distant metastasis confirmed by intraoperative exploration or postoperative pathology, including liver, pelvic cavity, ovary, peritoneum, distant lymph node metastasis, etc.
- (4) Patients who need combined organ resection as determined by intraoperative exploration.

(5) Patients who request to withdraw from this study cohort for various reasons after being enrolled in the study, or who cannot complete the study plan and follow-up for various reasons.

The data of patients who withdrew from the study were not used, and these patients were not allowed to re-enter the study.

6. Study treatment grouping

Experiment group: Total laparoscopic intracorporeal anastomosis group (IA group)

The tumor is resected according to surgical specifications for radical colon cancer surgery. Mesentery resection is performed under laparoscopy, and anastomosis is completed under laparoscopy. A small incision is made to extract the specimen after the anastomosis is completed.

Control group: Laparoscopy assisted extracorporeal anastomosis group (EA group)

The tumor is resected according to surgical specifications for radical colon cancer surgery. A small incision is made in the middle of the abdomen to trim the mesentery, remove the specimen, and complete the anastomosis. After completing the anastomosis, the incision will be sutured.

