12.2 Analytical population

12.2.1 Full analysis set

The primary outcome will be comparatively analyzed based on “modified intention-to-treat (mITT)”. In the mITT analysis, patients will be analyzed according to their randomization allocations. If patients randomly assigned to the IA group actually receive EA during surgery, they will be analyzed according to the IA group in mITT analysis. If patients randomly assigned to group EA actually receive IA during surgery, they will be analyzed according to group EA. Patients who meet the exit criteria after randomization will not be included in the mITT population.

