4.2 Analysis populations

4.2.1 Modified intention-to-treat (mITT) population

In the mITT analysis, patients will be analyzed based on their randomization allocations. If patients randomly assigned to the IA group receive EA during surgery, they will be analyzed within the IA group in the mITT analysis. If patients randomly assigned to group EA receive IA during surgery, they will be analyzed according to group EA. Patients who meet the exit criteria after randomization won't be included in the mITT population.

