4.2.3 As-treated (AT) population

In the AT analysis, we'll analyze patients according to the actual treatment they received instead of the allocated plan for random groups.

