4.6 Secondary endpoints

The secondary endpoints will be compared between groups in the mITT population, PP population, and AT population.

- Operating time, continuous variable, measured in minutes;
- Total blood loss during operation, continuous variable, measured in milliliters;
- Conversion to open surgery, categorical variable;
- Postoperative complications, categorical variable. It will be analyzed according to the overall occurrence. The occurrence of its subtype (anastomotic leakage, bowel obstruction, etc.) will also be analyzed. Additionally, Clavien–Dindo classification will be analyzed (\leq grade II, \geq grade III). (3)
- Completeness of specimens, categorical variable. It is evaluated according to the West classification (mesocolic plane, intramesocolic plane, and muscularis propria plane).(4)
- Number of lymph nodes dissected, continuous variable.
- The pathological TNM stage (as per the American Joint Committee on Cancer

Cancer Staging Manual, 8th edition), categorical variable. The T stage, N stage, and TNM stage will be analyzed separately.

- Postoperative recovery, continuous variable. It includes the time to first flatus, the time to first defecation, the time to start food intake, and the postoperative hospital stay. Additionally, the time to first ambulation and the time to remove the abdominal drainage tube, which are not included in the study protocol's design, will also be analyzed. These are measured in days.
- Length of incision, continuous variable. It is measured in millimeters.
- Visual analog score (VAS) of pain, it will be analyzed as categorical variable: no to mild pain (0–3 points); moderate pain (4–6 points), and severe pain (7–10 points).
- 3-year DFS: DFS is defined as the time from randomization until the occurrence of local recurrence, distant metastasis, or death from the tumor, whichever comes first. It is measured in months. For patients who are lost to follow-up, DFS will be censored at the time of the last available tumor assessment before the missing assessments.
- 5-year OS: OS was defined as the time from randomization to death due to any cause. It is measured in months. For patients lost to follow-up, OS will be censored at the time of the last available follow-up prior to the missing assessments.

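### Complications recorded in operated patients who later exit are dropped from the mITT harm comparison, and those of patients who withdraw are dropped from every analysis set

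*Combined protocol and SAP*

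**What the plan says.** All references are to protocol v2.1 and SAP v1.0.

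- **What counts as harm.** Protocol 9.1: "Adverse events studied include intraoperative secondary injuries in patients and serious complications and deaths within 30 days after surgery". Safety is a secondary purpose (3.1.2).
- **Where harm is compared.** SAP 4.6 lists postoperative complications (overall, by subtype, and grade II or lower against grade III or higher). On sets it states: "The secondary endpoints will be compared between groups in the mITT population, PP population, and AT population". No safety population is defined.
- **Who is left out of mITT.** Protocol 12.2.1: "Patients who meet the exit criteria after randomization will not be included in the mITT population". SAP 4.2.1 has the same rule.
- **What the exit criteria are.** Protocol 5.3 lists five. Criterion 3 is distant metastasis found at exploration or on postoperative pathology. Criterion 4 is combined organ resection found necessary at exploration. Criterion 5 covers patients who ask to withdraw "or who cannot complete the study plan and follow-up for various reasons".
- **What happens to the data.** Protocol 5.3: "The data of patients who withdrew from the study were not used, and these patients were not allowed to re-enter the study". Protocol 7.4, on a patient who insists on withdrawing: "Clinical information relating to this patient will not be included in any data analysis related to this trial".
- **The AT set.** SAP 4.2.3 says only that the trial will "analyze patients according to the actual treatment they received instead of the allocated plan for random groups". It does not mention exits.

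**The concern.** A harm comparison should include everyone exposed to the operation, for as long as they were observed. Here a patient can have the assigned operation, suffer a complication that is recorded, and then leave the comparison because of something that happened or was discovered later.

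For metastasis and combined resection the reason lies mainly in the tumour, so randomisation should spread these exits over both arms. For criterion 5 the reason can be the harm itself: a patient with a bad postoperative course may be more likely to withdraw or to miss the rest of follow-up. If that happens more in one arm, the mITT complication rates describe only the patients who stayed, and randomisation gives no protection. Since the protocol also bars the use of withdrawn patients' data, the events cannot simply be added back in a later table.

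**Working it through.** **1. Which exits can follow the start of surgery, and where their harms go**

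| Exit criterion (protocol 5.3) | Can arise during or after surgery? | mITT | AT |
|---|---|---|---|
| 3. Metastasis at exploration or on pathology | Yes | Excluded | Not stated; no exclusion written |
| 4. Combined resection at exploration | Yes | Excluded | Not stated; no exclusion written |
| 5a. Withdrawal on request | Yes | Excluded | Barred by 5.3 and 7.4 |
| 5b. Plan or follow-up not completed | Yes | Excluded by 12.2.1; SAP 4.5 and 5 instead treat 30-day non-completers as missing data | Not stated |

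Row 5a is clear: those harms are lost from every set, PP included. Rows 3 and 4 are lost from mITT, the only set that keeps patients in their assigned arm whatever operation they received. Row 5b is a conflict inside the documents. If every non-completer has already left mITT, the SAP's missing-data rule for the 30-day endpoint has little left to act on there.

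**2. The plan's own sample size, to fix the drop-out allowance**

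Inputs (protocol 12.1, SAP 3): SSI 13.3% with EA and 8.0% with IA, margin 5 points, one-sided 0.025, power 0.80, drop-out 20%.

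- Distance to the margin: 0.05 + 0.133 − 0.080 = 0.103.
- n per arm = (1.960 + 0.842)² × (0.080 × 0.920 + 0.133 × 0.867) / 0.103² = 7.849 × 0.1889 / 0.01061 = 139.8, so 140.
- 140 / 0.80 = 175 per arm, 350 in total. This reproduces the plan.
- Allowance: 175 − 140 = 35 per arm. Each event is 1/175 = 0.6 points of an arm's rate.

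**3. Range of possible effect (all exit and event rates assumed)**

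Let e be the share of operated patients who exit and r their rate of grade III or higher events, against 5% in those who stay. The share of serious events missing from mITT is e·r / [(1 − e)·0.05 + e·r].

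| e | r = 5% | r = 10% | r = 20% |
|---|---|---|---|
| 2% | 2% | 4% | 8% |
| 5% | 5% | 10% | 17% |
| 10% | 10% | 18% | 31% |
| 20% | 20% | 33% | 50% |

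The last row takes every allowed drop-out as an operated exit, so it is an upper bound within that allowance.

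**4. Effect on the difference between arms (at that upper bound)**

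Intervals are Newcombe's, built from the Wilson limits l and u of each arm: lower = d − √[(p₁ − l₁)² + (u₂ − p₂)²], upper = d + √[(u₁ − p₁)² + (p₂ − l₂)²].

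| Grade III or higher, IA v EA | Difference, points (95% CI) | Fisher p |
|---|---|---|
| mITT: 7/140 v 7/140 | 0.0 (−5.6 to 5.6) | 1.00 |
| All operated, exits unrelated to harm: 9/175 v 9/175 | 0.0 (−5.0 to 5.0) | 1.00 |
| All operated, 3/35 IA exits and 0/35 EA exits with an event: 10/175 v 7/175 | 1.7 (−3.1 to 6.6) | 0.62 |
| All operated, 5/35 and 0/35: 12/175 v 7/175 | 2.9 (−2.1 to 8.0) | 0.35 |

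The last two rows are deliberately one-sided, with no events among EA exits. They show the direction and order of size and do not forecast a result. Every interval includes zero.

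**The case against.** The strongest reply has four parts.

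- **AT may already do part of the job.** The exit exclusion is written into mITT and not into AT, so the natural reading keeps metastasis and combined-resection exits in AT. This largely stands. A reader might infer that all exits vanish from every set; the documents support that only for withdrawn patients. But AT does not say that it keeps the others, and it groups by treatment received, so it cannot give the comparison by assigned arm.
- **Death is not a failure to complete follow-up.** A reader might infer that criterion 5 removes patients who die. Protocol 15 lists death as a follow-up outcome, grade V on the complication scale is death, and overall survival counts it. The sensible reading keeps deaths. What stands of the concern is that criterion 5 names no exception, and that its wording on non-completion conflicts with the SAP's missing-data rule.
- **Somebody does look at harm by arm.** Under protocol 12.6 the DSMB reviews adverse events yearly and alerts the steering committee chair if they are unbalanced between groups. So it would be wrong to say that harms go uncompared. This is monitoring during the trial, however, and does not supply the final analysis.
- **The illustrations are contrived.** True: some exits will precede surgery, and the imbalance is assumed. They are kept only to show scale.

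A reader might also want to add that the SAP has no row for intraoperative injury and no laboratory summary as in protocol 8.2.2. Both are gaps in reporting, and neither is a listed endpoint. Injuries that cause bleeding, conversion or a complication are partly captured in SAP 4.6. For the laboratory item, the abstract asks for day-30 tests while Table 1 ticks blood tests at screening only, and a single day-30 value could not meet the minimum-or-maximum rule in 8.2.2. They are optional notes and no part of this point.

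**Conclusion.** The point holds in limited form. Followed literally, the plan loses recorded harms of operated patients who withdraw from every analysis, and loses those of patients who exit for metastasis or combined resection from the comparison by assigned arm. Whether non-completers are removed or counted as missing is unresolved.

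The size is unknown. If exits are unrelated to harm, the cost is precision only: at the upper bound the interval half-width is 5.6 points in place of 5.0. If they are related to harm and unequal between arms, a few events move the difference by 1.7 to 2.9 points under the assumptions in step 4, which also take all 175 per arm as operated on. Metastasis and combined-resection exits should be mostly balanced, so the risk of bias lies mainly in withdrawal or non-completion that follows a complication.

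The documents do not support a claim that deaths or grade III or higher complications are missing from the SAP, since SAP 4.6 covers them. Nor does this point bear on the margin, the sample size or the primary test. It is a cheap improvement that should be made to the safety analysis.

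**What to change.** 1. **Add a safety set to the SAP:** all randomised patients whose operation began, shown by assigned arm and by treatment received. Count any complication, and grade III or higher, up to exit, withdrawal or day 30. Report n, %, risk difference and 95% CI, as description only.
2. **Clarify criterion 5:** state that a death or a complication is never an exit, and that 30-day non-completers are handled as missing data under SAP 4.5 and 5.
3. **State in SAP 4.2.3** whether AT keeps patients who exit under criteria 3 and 4.
4. **Amend protocol 5.3 and 7.4 prospectively,** with ethics approval as needed, so that data recorded before exit are kept unless the patient refuses. Report refusals by arm.

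The cost is one SAP section, a few table rows and the amendment; complications are already recorded. There are two downsides. Patients who exit may have incomplete 30-day follow-up, so theirs are minimum counts. And since leaks and other SSIs are also complications, the safety rows may show events that are absent from the primary mITT table, which a footnote should explain.

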9.2 Severe adverse event

A serious adverse event includes any of the following adverse medical events: 1) events leading to death; 2) life-threatening events; 3) requiring hospitalization or prolonged hospitalization of patients; 4) Causing persistent or significant disability, or incapacity for conduct.

9.3 Severity assessment

The severity of adverse events will be assessed using the Clavien—Dindo grading criteria for complications.

9.4 Relevance judgement

Determining the correlation between adverse events and surgical interventions will be made by researchers subjectively.

10. Data processing and storage

All relevant clinical data including demographic and medical information will be collected from the electronic medical record. The collected data will be encoded to protect the privacy of all participants and then be entered into an electronic case report forms (eCRFs) by trained research assistants in each sub-center. Double data entry will be performed to ensure that the data collected are accurate and verifiable from source documents. Input rules including field and range checks will also be set to minimize data entry errors. The research coordinator will periodically check the data distribution, verify outliers, and track missing data to improve data integrity and data validation. Data storage and backup will be managed by the edocdata platform (<https://jlcrc.edocdata.com/>), which will track all changes to the data and retains a history for each variable. Unauthorized persons or institutions will not be able to access any data stored on this server. When the trial is completed, the data will be locked and stored on edocdata platform, after which the researchers can no longer modify the data. Both paper and electronic documents will be preserved for at least 5 years after publication.

11. Quality management

Research center participation criteria: Surgeons involved in this study must complete at least 100 cases of laparoscopy-assisted left colectomy and have a minimum of 20 cases of intraoperative anastomosis in laparoscopy-assisted left colectomy. This study establishes a trial steering committee (TSC). The TSC is composed of surgeons with at least 10 years of experience in colorectal cancer surgery. Before enrolling in the research center, participating centers should provide surgical videos of two consecutive IA cases and two EA cases by the same operator recently to determine if the surgery quality meets expectations and if they can qualify as enrolment units. The evaluation method is the Delphi method.

Evaluation of surgical quality during research: Surgery quality is assessed using videos and photographs. Surgical teams are required to take photographs of the laparoscopic investigation of the tumor site, surgical area after lymph node removal, and the anastomosis. The TSC evaluates the videos and photographs to assess surgical quality and ensure compliance with the allocated intervention. Any surgical procedures deviating from the randomized allocation plan are documented. If participating centers cannot obtain imaging data, they must document the reason for not being able to leave a video or photo.

Surgeons participating in the trial are required to record the surgical procedure and explain any surgical procedures that deviate from standardized procedures. The trial steering committee will evaluate the enrollment situation and quality of enrolled cases at each center every half a year and supervise and control the quality of enrolled cases at each center.

12. Statistical analysis

12.1 Method for determining sample size

This study is a multicenter, randomized, controlled, noninferiority trial specifically designed for patients within the age range of 18 to 80 years old who are diagnosed with left-sided colon cancer. We adjusted the sample size according to our latest published multicenter retrospective data(19). We expected that the incidence of overall surgical site infection following extracorporeal anastomosis left colon cancer surgery stands at 13.3%, while the incidence of SSI after intracorporeal anastomosis is 8.0%. When there is an absolute risk difference in the SSI rate of more than 5% within 30 days after surgery, intracorporeal

anastomosis is regarded as inferior to extracorporeal anastomosis. Consequently, the sample size for this study is calculated based on non-inferiority, considering an absolute risk difference of 5%, a one-sided level of significance of 0.025, a ratio of 1:1, a power of 0.80, and a 20% drop-out rate. In total, 350 patients are required for this study, with 175 patients in the experimental group and an equal number of 175 patients in the control group.

